11.1	Institutional Review Board (IRB) Review	14
11.2	Informed Consent Forms.....	15
11.3	Participant Confidentiality.....	15
11.4	Study Discontinuation	15
12	ETHICAL CONSIDERATIONS	15
13	COMMITTEES.....	15
14	PUBLICATION OF RESEARCH FINDINGS	15
15	REFERENCES	16

PRÉCIS

Study Title

5-Cog Battery to improve detection of cognitive impairment and dementia

Objectives

Despite the availability of numerous cognitive assessment tools, cognitive impairment related to dementia is frequently under-diagnosed in primary care settings, and is a more prevalent problem among older African-Americans and Hispanics than among older whites. To overcome the technical, cultural and logistic barriers of current cognitive screens and dementia care in primary care settings we propose to validate a 5-minute cognitive screen (5-Cog) coupled with a decision tree to identify persons at high risk of developing dementia in multi-ethnic primary care populations with socio-economic challenges. The primary objective is to test the ability of the 5-Cog battery and decision tree paradigm to improve dementia care in primary care patients with cognitive concerns.

The 5-Cog battery includes the Picture based Memory Impairment Screen (PMIS),¹ Motoric Cognitive Risk Syndrome (MCR) diagnosis,²⁻⁴ and a brief non-memory picture based test (Symbol Match). Our cognitive assessment algorithm will sort patients with ‘cognitive impairment’ from those with ‘no cognitive impairment’. Moreover, it is coupled with a decision tree to guide clinicians through the follow up on any 5-Cog results.

Design and Outcomes

We propose to conduct a single-blind randomized clinical trial (RCT) in 1,200 primary care patients age 65 and older presenting with cognitive complaints. Non-medical professionals will administer the 5-Cog in the intervention group and a 5-minute health literacy and grip strength assessment in the active control group.

Interventions

The interventions will be given after randomization and before the patients sees the physician. After completing the intervention or control assessments, the tester will provide results to the treating physician with follow-up recommendations based on the decision tree.

Participants randomized to the active control will receive a health literacy questionnaire, the Short Assessment of Health Literacy (SAHL) and grip strength assessment to match time (5 minutes), tester exposure and decision tree procedure in the 5-Cog arm. To parallel the study procedures and flow in the 5-Cog arm, a decision tree for the active control arm will also be created. Results of the control screen and the decision tree will be presented to the physicians at the same visit.

Sample Size and Population

Our testing will be carried out in an urban, multi-ethnic Bronx patient population. We will use a randomized block design to place 1,200 patients into either 5-Cog or control groups. Patients will be stratified by gender and age (< or >75 years).

STUDY TEAM ROSTER

Administrative Core:

Principal Investigator ([name]): will head the Management Team and its Cores. He will assign responsibilities to team members and integrate their feedback to ensure timely progress. To this end, he will chair regularly scheduled, full-team meetings with standing agendas and predictable cycles of reports. [name] will also hold smaller, Core meetings in order to manage specific concerns and unforeseen issues. If necessary, he will also meet individually with team members on an *ad hoc* basis. [name] manages programs by promoting a sense of participation and ownership by all investigators and staff. He is strongly committed to an open management style, encouraging staff to identify problems and propose solutions.

Project Manager ([name]): will assume fiscal and administrative management, including supervising budgets, tracking adherence to timelines, and maintaining collaborative relationships among the PI, investigators and cross-consortium coordinating team (CCCT) members. She will also be responsible for coordinating with members of the CCCT to conduct pilot studies and facilitate sharing of data and paradigms. She will prepare reports for the NIH and the IRB.

1.1 Primary Objective

The 5-Cog battery and decision tree will improve dementia care in primary care settings for patients with cognitive concerns. Improved dementia care will be measured by new Mild Cognitive Impairment syndrome (MCI) or dementia diagnoses, laboratory investigations to rule out reversible causes of cognitive impairment, new dementia medication prescriptions, and specialist referrals for dementia care, and will be tracked using the electronic medical record (EMR) system.

1.2 Secondary Objectives

Utilization (emergency room visits and hospitalizations) for patients in both arms will be tracked and reviewed at regular intervals throughout the study period. Utilization is defined in terms of specialty visits, emergency room visits, and hospitalizations up to 12 months following the screening visit. This will be tracked via the EMR in both groups.

2 **BACKGROUND AND RATIONALE**

2.1 Background

Cognitive impairment related to dementia is frequently under-diagnosed in primary care settings despite the availability of numerous assessment tools.⁵⁻⁷ Missed detection delays treatment of reversible conditions as well as provision of support services and critical planning.⁸ This problem is more prevalent among older African-Americans and Hispanics than among older whites.⁵⁻⁷

Picture Memory Impairment Screen (PMIS): A major limiting factor in identifying dementia in health disparate populations are the lack of cognitive screens that account for cultural differences and variable literacy rates. Also, many cognitive screens are lengthy and not designed for non-specialist use, limiting their application in primary care. The Memory Impairment Screen (MIS) is a brief, 4-item delayed free- and cued-recall test that was developed and validated in an urban U.S. population,⁹ and recommended for dementia screening.¹⁰⁻¹² However, the MIS requires minimum reading skills, which limits its use in low literacy populations.¹¹ To address limitations of the MIS and other language-based cognitive screeners,¹⁰ we developed the PMIS that uses pictures. The PMIS minimizes educational bias, and expands the scope of dementia screening to low literacy populations. In our validation study in India,¹ the PMIS discriminated between cognitively normal older adults and those with dementia, regardless of age, sex, education or depression.¹

The PMIS takes 4 minutes, which includes a minimum 2-minute delay period between picture presentation and recall. During this delay, another cognitive test can be given as an interference task, which prevents patients from using strategies such as mentally rehearsing items that may lead to false negative ‘normal’ performance. In the 5-Cog, we will fill the 2-minute interference period with the MCR diagnosis and paper-based Symbol Match Test. We developed highly reliable alternate forms of the PMIS, which enable repeated administration.¹² Professionals and non-professionals (health aides with 10 years schooling) successfully administered the PMIS in rural and urban populations in India and USA.^{13, 14} High inter-rater reliability was seen between administration of PMIS by clinicians and nurses.¹⁵ The PMIS picture items were administered on a computer screen

and using cards.¹⁶ These findings support the feasibility of using the PMIS in various settings and by personnel with different levels of expertise.

Motoric Cognitive Risk Syndrome (MCR): Many pre-dementia syndromes based on cognitive tests or biomarkers have been proposed^{17, 18} but their requirement for specialized equipment and medical professionals to conduct examination limits feasibility in resource-poor primary care settings. Increasingly, the simultaneous existence of motor and cognitive impairments has been recognized as an important clinical marker of brain pathologies. Hence, incorporating measures of motor function (gait speed) into dementia risk assessments may improve predictive power.¹⁹ We described the MCR syndrome; characterized by cognitive complaints and slow gait.^{4, 20} The MCR criteria are similar to those used for Mild Cognitive Impairment syndrome (MCI).^{21, 22} We substitute the cognitive test criterion in MCI with gait speed in MCR, but retain the remaining MCI criteria (cognitive complaints and absence of dementia). *MCR diagnosis is easy to implement because it only requires verification of cognitive complaints and a stopwatch to measure gait speed over a fixed distance.*

In a multi-country study of over 26,000 persons aged 60 and older, MCR affected 1 in 10 participants.²⁰ Advancing age was associated with MCR but there were no sex differences in prevalence. Participants with MCR had a higher disease burden and performed worse on cognitive tests than non-MCR participants.²⁰ MCR was associated with a 70% increased risk of developing cognitive decline (on MMSE).²⁰ The association of MCR with cognitive impairment was robust even when the analysis was restricted to cognitively healthy adults (Mini-Mental State Examination scores ≥ 28), supporting MCR as a very early clinical marker of cognitive decline.²⁰ MCR diagnosis in older adults was associated with deficits in executive function, attention and language as well as overall cognitive status.²³ In 4 longitudinal cohort studies, participants with MCR were twice as likely to develop dementia, and were at 2.2 times the risk of developing Alzheimer's disease specifically.^{20, 24, 25} MCR predicted dementia with greater accuracy than its individual components of either slow gait or subjective cognitive complaints.²⁰ Because MCR is diagnosed independently of cognitive tests, we avoid redundancy (diagnostic circularity) by not using the same tests to define both pre-dementia and dementia syndromes. In our multi-country study, clinical overlap between MCR and MCI cases was only 39%; indicating that the presence of either syndrome alone failed to identify a large pool of at-risk seniors.² From a diagnostic perspective, MCR offers several benefits over other pre-dementia assessments. Gait speed has high reliability between different protocols,^{26, 27} excellent validity in predicting health outcomes,^{26, 27} and is recommended as a geriatric vital sign.²⁸ Non-professionals can easily be trained to measure gait speed in a minimal amount of time and without expensive equipment, making screening cheap and efficient in clinical settings. Hence, timing gait and asking brief cognitive questions to define MCR is practical and feasible in resource-poor settings, and can help streamline high-risk individuals for further investigations. The entry criteria for our study requires presence of cognitive complaints. Hence, MCR diagnosis procedure in the 5-Cog arm only requires measurement of timed gait over a fixed distance, and determination of slow gait using previously established cutscores in our population.

Paper-based Symbol Match Test: Match is a tablet-based test of executive functions and speed developed by the CCCT at University of California San Francisco (UCSF). Our team has created a paper-based version of the Symbol Match stimuli to act as a screening tool

which may identify patients with cognitive impairment who were not identified by the PMIS or MCR.

2.2 Study Rationale

Our group has two decades of experience developing tools to detect dementia in health disparate populations. Notably, we developed the PMIS, which is a brief cognitive screener that relies on culture fair pictures and does not need to be administered by a medical professional.¹ The PMIS demonstrated sensitivity of 95% and a specificity of 99% for detecting dementia in a low-literacy population in India.¹ We also validated the MCR diagnosis in multiple cohorts in many countries.²⁻⁴ This highly accessible clinical test relies on the presence of slow gait and cognitive self-complaints to identify individuals at high risk of converting to dementia. Both the PMIS and the MCR are highly sensitive and specific first-line assays that can be followed up with more thorough and complex cognitive testing.²⁻⁴

Building on our work, we propose to validate a 5-minute screen (**5-Cog**) to identify persons with or at high risk of developing dementia, and to flag them for further evaluation. We propose to do this in multi-ethnic Bronx primary care populations with socio-economic challenges. The 5-Cog battery will include the PMIS, MCR syndrome diagnosis, and brief non-memory picture based test, Symbol Match.

The 5-Cog will sort out patients with or at high risk of developing ‘cognitive impairment’ from those with ‘no cognitive impairment’. The 5-Cog battery will overcome many of the implementation barriers of previous cognitive screens;^{13, 29, 30} it will be fast, low cost, easy to implement (requires only pen, paper and stopwatch), administered by non-clinicians (research assistants) after minimal training, not educationally or culturally biased, not confounded by depression and will not require informants.

3 STUDY DESIGN

We propose to conduct a single-blind RCT to validate the 5-Cog battery and decision tree (Fig. 1). The trial will span 42 months and involve an ethnically diverse Bronx primary care population of 1,200 older patients with cognitive concerns (Fig. 2). We chose an active control (health literacy and grip) to balance time and tester exposure in the 5-Cog group. Our primary outcome is improved dementia care, which is an outcome that informs health decisions and is valued by primary care clinicians, older patients and their caregivers. We bring together an inter-disciplinary team with major aging and clinical trial experience. We have developed partnerships with clinicians in our primary care clinic site.

[figure not shown]
Design considerations: We will take a pragmatic, real world approach in our trial. We will not ask physicians to deny patients any procedures offered routinely. For instance, clinicians have access to the PMIS and other cognitive screeners (not included in the 5-Cog screen) in our EMR. We will not ask clinicians to avoid using these screeners in enrolled patients. But we will track cognitive screener use by clinicians in control and 5-Cog arms via the EMR. We hypothesize that time constraints and other barriers as well as the absence of the MCR and Symbol Match procedure in the EMR will limit use and efficacy of cognitive screeners by primary care physicians. The proportion of older women is higher than men in our clinics and aging studies.^{3, 14, 31} Consistent with our pragmatic approach,

we will not strive for equal sex distribution within a study arm, but balance sex distribution by selecting gender as a stratification variable. There is no trial design without weakness and we will clearly state these in any publications.

Recruitment: We will enroll 1,200 older patients with cognitive concerns (reported by patient or noted by caregivers or clinic staff) over 30 months; estimated enrollment rate is 8-10 per week. This enrollment rate conservatively assumes a >50% refusal rate from potentially eligible participants. Our enrollment rate in our pilot study at the same clinical site was about 6-8 per week when participants were asked to complete a longer battery of assessments. While we anticipate that many potential participants may be attending our primary care clinics for their Medicare Annual Wellness visit,¹² we will also recruit patients attending the clinics for other medical reasons. Montefiore Medical Center is the main healthcare system for Bronx county; one of the most ethnically diverse communities in the nation with an elderly population of 140,000 (U.S. census data). Patients age 65 and older account for >20,000 primary care visits at Montefiore annually; ensuring an adequate pool for recruitment. The non-clinician tester will approach all patients age 65 and over attending our primary care clinic sites. Those expressing interest will be screened at the same visit to determine eligibility. Information regarding demographics, socio-economic status and medical illnesses will be collected.

Primary Outcome: Our primary outcome is **improved dementia care**. This outcome is collected prospectively from EMR and related medical records by data analysts (blinded to study arm allocation and test results), and do not require patient interviews. This primary outcome is defined as meeting any one of the following endpoints within 90 days of the clinic visit at which the patient was randomized. Similar composite endpoints to define

Figure 1. 5-Cog Flow & Decision Tree

dementia care have been used in several prior clinical trials in cognitively impaired patients.³²⁻³⁶

1. New diagnosis of dementia (relevant ICD-10 codes) or MCI (331.83) documented in the EMR. The recent DSM-V criteria³⁷ include categories of ‘major neurocognitive disorder’ and ‘mild neurocognitive disorder,’ which overlap with dementia and MCI. These categories will also be included but a recent internal audit indicated that they are as yet not in widespread use in our primary care clinics (cf. specialty clinics).
2. Tests ordered for reversible causes of cognitive impairment as recommended by the published guidelines of professional societies (e.g. thyroid function tests, B-12 level, CT or MRI scans).^{15, 38-41}
3. New prescriptions for dementia medications in EMR.
4. Referral for cognitive/dementia evaluation by specialists (Neurology, Geriatrics or Psychiatry) in EMR.

Secondary/exploratory outcomes: Health care utilization data (*secondary outcome*) is abstracted from EMR. Additional tests (described below) take approximately 60 minutes of participants’ time. To avoid interrupting clinic flow, these tests will be done at the same visit as the enrollment, but after the patient sees their clinician. These tests are *exploratory outcomes* used to generate new hypotheses or provide insights into 5-Cog efficacy.

- a) **Health care utilization (secondary outcome):** Utilization (emergency room visits and hospitalizations) for patients in both arms will be tracked up to 12 months from the clinic visit at which the patient was randomized and reviewed at regular intervals by data analysts throughout the study period. The data analysts will have no participant contact and be blinded to study assignment. The EMR system is in place in our institution. All visit notes and diagnoses are to be entered within 48 hours of the encounter. A series of electronic reminders is sent to clinicians to complete delinquent entries. Patients in both arms will be covered by risk or shared savings reimbursement arrangements Montefiore has with private health insurance companies or will be fee-for-service Medicare beneficiaries attributed to the Montefiore Next Generation Accountable Care Organization.⁴²⁻⁴⁴ Montefiore either processes or has access to claims data for these patients, enabling analysis of encounters and costs through the Montefiore EMR and reports received monthly from CMS. The detailed claims-level data will allow for tracking and analysis of the utilization of numerous healthcare services. A significant amount of data on care and services that patients receive from providers outside of Montefiore will also be available for inclusion in our analyses.
- b) **Neuropsychological Battery (exploratory outcome):** The battery will take 60 minutes to complete and will include the measures below (Table 1). The tests are selected from those used for diagnostic testing in our dementia clinic, and with established norms for different ethnic groups and educational levels.¹⁴ The battery will be supervised by [name] (Cognitive Core); blinded to 5-Cog results. The battery is administered in English or Spanish to probe general mental status (MoCA) as well as specific cognitive domains, particularly memory (Hopkins Verbal Learning Test-R⁴⁵), processing speed (Symbol Digit Modalities Test⁴⁶), language (letter fluency,^{47, 48} category fluency,⁴⁸ Boston Naming Test⁴⁸), and visuo-spatial abilities (clock drawing¹²).⁴⁹ For ethical reasons, if results from the neuropsychological testing are in the dementia range, [name] will inform the treating physician after the 90-day window to determine improved dementia care outcomes.

Table 1. Neuropsychological Assessments

Domain	Tasks
Mental Status	MoCA
Premorbid Estimate/ Reading ability	Wechsler Test of Adult Reading (WTAR)/ Word Accentuation Test (TAP)
Memory	Hopkins Verbal Learning Test- R(HVLT-R)
Naming	Boston Naming- Short Form
Fluency	Controlled Oral Word Association Test (FAS); Animals
Timed Transcription	Symbol Digit Modalities Test
Clock	Clock Drawing Test
Mood	Geriatric Depression Scale-30 item

c) **Advance care planning (exploratory outcome):** We will explore whether 5-Cog screening leads to higher rates of advance care planning such as referrals to social work or Alzheimer's Association or having health care proxies or living wills recorded in the EMR.

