4.2 Exclusion Criteria

1) Prior diagnosis of dementia or MCI as ascertained by ICD-10 codes or the presence of prescription for anti-dementia medications (cholinesterase inhibitors or Memantine) in EMR. Patients with a diagnosis containing any of the following terms will be excluded:

- a. “Dementia”
- b. “Mild Cognitive Impairment”
- c. “Alzheimer’s Disease”
- d. “Creutzfeldt-Jakob Disease”
- e. “Major Neurocognitive Disorder”
- f. “Minor Neurocognitive Disorder”

Patients with any of the following medications documented in their EMR will be excluded (generic = brand):

- a. Donepezil = Aricept
- b. Memantine = Namenda
- c. Rivastigmine = Exelon
- d. Galantamine = Razadyne
- e. Donepezil and Memantine = Namzaric

2) Adults who are permanent residents of a nursing facility.

3) Patients who do not speak English or Spanish.

4) Patients who are not seeing a primary care physician at the clinic that day.

5) Patients who are blind, deaf or cannot hear loud voice even with hearing aids.

Recruitment, enrollment, and participation of participants in this project are not limited by gender, skin color, racial/ethnic group, or economic status. We will monitor recruitment and retention patterns to ensure adequate representation of women and minorities. Since this study focuses exclusively on geriatric syndromes, it will not include children.

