9.5 Data Analyses

We will examine data for potential outliers and analyze the robustness of our findings

against them. We will perform per-protocol analysis to assess the sensitivity of our findings to protocol deviations. Furthermore, the impact of baseline imbalance will be determined by comparing the analysis outcomes with and without controlling for baseline attributes. Chi-square test will be used to compare ‘improved dementia care’ outcome within 90 days post-intervention between the intervention and control groups. Logistic regression model adjusted for covariates will also be used. We will use **intention to treat analysis**.⁵⁷ Pre-specified baseline covariates to account for **confounders** in the planned analysis include age, gender, education, and chronic illnesses. Baseline distribution of covariates will be compared to assess adequacy of randomization. We do not discount residual/unmeasured confounding – though this is more of an issue in observational studies without randomization. We will report adjusted and crude estimates of associations to assess confounding, and discuss limitations of the study.

Primary outcome: Chi-square test will be used to compare ‘improved dementia care’ outcome within 90 days post-intervention between the intervention and control groups. Logistic model adjusted for covariates will also be used.

Heterogeneity of treatment effect (HTE) is the nonrandom, explainable variability in the direction and magnitude of treatment effects for individuals within a population. The main goals of HTE analysis are to estimate treatment effects in clinically relevant subgroups and to predict whether an individual might benefit from a treatment. In this RCT, we will specifically address HTE due to gender (male/female), ethnicity (African-American/Hispanic/Caucasian) and education (less than high school/ high school graduate). Treatment effects in these subgroups will be evaluated using stratified analysis. Alternative, an interaction term between the subgroup characteristic and treatment group will also be tested.

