Secondary outcome: Utilization is defined in terms of specialty visits, emergency room visits, and hospitalizations up to 12 months following the screening visit. This will be tracked via the EMR in both groups. The rates of utilization will be compared between the two groups using analytical approaches described for the primary outcome. We will also compare ‘days free of utilization’ (number of days from screening to first episode of health care utilization over follow-up) in both groups using linear mixed effect and survival models.^{58, 59}

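### The proxy and living-will part of the advance-care-planning outcome is worded as an EMR status, so read literally it counts documents filed before randomization and dilutes the arm difference

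*Combined protocol and SAP*

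**What the plan says.** Section 3(c) is the only definition of the advance-care-planning outcome. It is labelled exploratory and framed as a causal question: "We will explore whether 5-Cog screening leads to higher rates of advance care planning". The listed examples are referrals to social work or to the Alzheimer's Association, and "having health care proxies or living wills recorded in the EMR". No start date, end date or baseline status is given.

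The primary outcome in the same section is worded differently. Component 1 is "New diagnosis of dementia (relevant ICD-10 codes) or MCI (331.83) documented in the EMR" and component 3 is "New prescriptions for dementia medications in EMR", both within 90 days of the randomization visit. Eligibility also looks back through the EMR: Section 4.2 excludes patients with "Prior diagnosis of dementia or MCI as ascertained by ICD-10 codes" or a prescription for a listed dementia drug.

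For the secondary outcome, Sections 1.2, 3(a), 9.4.2 and 9.5 all describe utilization looking forward only, up to 12 months from the visit. Section 9.5 says "The rates of utilization will be compared between the two groups using analytical approaches described for the primary outcome", and adds mixed-effect and survival models for days free of utilization. The pre-specified covariates "in the planned analysis include age, gender, education, and chronic illnesses". Section 9.5 also plans a comparison with and without control for baseline attributes, but does not name them. On data sources, Section 3(a) says "The detailed claims-level data will allow for tracking and analysis of the utilization of numerous healthcare services". It does not mention data from before enrollment.

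**The concern.** A proxy or living will filed before the visit cannot be a result of the screen. Patients are 65 or older and already registered at the institution (Section 4.1), so some are likely to have one, although the protocol does not say how many. If those records count, patients whose status cannot change sit in both numerator and denominator of both arms. The observed difference shrinks, and a real effect on new documents could be reported as no effect. Two analysts working from Section 3(c) could also extract different outcomes, one counting any document on file and the other only new ones.

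The utilization question is of another kind. A patient's emergency and hospital use in the year before randomization is a plausible predictor of use in the year after, and the plan neither extracts it nor adjusts for it. What is at stake there is some precision on the only secondary outcome.

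**Working it through.** **The plan's own figures.** Section 9.2 gives 600 per arm, 10% non-completion, two-sided 0.05 and 80% power, with detectable odds ratios of 1.46, 1.43 and 1.42 at control rates of 25%, 30% and 35%. With n = 600 × 0.90 = 540 per arm and a pooled-variance two-proportion test, the intervention rates are 32.7%, 38.0% and 43.3%, and power is 80.2%, 79.3% and 80.2%. The figures reproduce. They concern the primary outcome only; no power is stated for advance care planning or utilization.

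**Proxy and living-will part: inputs.**
- n = 540 per arm, carried over from the primary outcome's 90-day loss assumption (Section 9.2).
- New-record rates among patients without a document: 10% control, 16% intervention (assumed).
- Share b with a document on file at randomization: 20%, 40%, 60% (assumed).

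**Formulas.**
- Rate as written: b + (1 − b)p. The arm difference is therefore (1 − b)(0.16 − 0.10).
- Restricted outcome: rates p unchanged, with n(1 − b) per arm.
- Power = Φ{[|p₁ − p₀| − 1.96 √(2p̄(1 − p̄)/n)] / √(p₀(1 − p₀)/n + p₁(1 − p₁)/n)}, with p̄ the mean of the two rates.

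**Worked case, b = 40%.** As written, the rates are 0.40 + 0.60 × 0.10 = 46.0% and 0.40 + 0.60 × 0.16 = 49.6%. Power = Φ[(0.036 − 1.96 × 0.0304)/0.0304] = 22%. Restricted, n = 540 × 0.60 = 324 per arm, and power = Φ[(0.06 − 1.96 × 0.0264)/0.0263] = 62%.

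| On file (b) | Rates as written | Difference | Power as written | n per arm, none on file | Power restricted |
|---|---|---|---|---|---|
| 20% | 28.0% v 32.8% | 4.8 points | 40% | 432 | 75% |
| 40% | 46.0% v 49.6% | 3.6 points | 22% | 324 | 62% |
| 60% | 64.0% v 66.4% | 2.4 points | 13% | 216 | 46% |

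With nobody on file (b = 0) the two definitions coincide and power is 84%.

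**Sensitivity.** With 600 per arm, power is 44/24/14% as written and 79/67/50% restricted. At 540 per arm and b = 40%, assumed new rates of 5% v 10% give 17% and 68%; 20% v 28% give 35% and 66%. The pattern does not depend on one pair of rates.

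**Chance imbalance.** At 540 per arm and b = 40%, the arm difference in documents already on file has standard deviation √(2 × 0.4 × 0.6/540) = 3.0 points, against a diluted effect of 3.6 points.

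**Utilization.** In a linear model of a count, adjusting for prior use with assumed correlation r removes r² of the variance: 9% at r = 0.3 and 25% at r = 0.5. That formula does not carry over to the planned chi-square, logistic and survival analyses. A simulation of any use versus none was run as a guide (logistic model, 540 per arm, assumed gamma-Poisson counts, none of the four planned covariates included). Adding prior use raised power from about 83% to 84% at correlation 0.28, and from 62% to 68% at 0.46. Those gains would shrink further to the extent that the chronic-illness covariate already carries the same information.

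**The case against.** The strongest reply is that the protocol nowhere says pre-existing documents will be counted. Asking what screening leads to fits documents recorded after the visit, and the investigators may have meant exactly that. This stands as far as intent goes. A reader might infer that the plan deliberately scores old documents as successes; the text supports only that it fails to rule them out.

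Second, the calculation covers one part of the outcome. Referrals come first in the list and are events, so they are less affected, although they too lack a window. The rates and on-file shares are assumed, and the 540 is borrowed from the primary outcome. All of this stands, and the power figures should not be read as power for the whole advance-care-planning outcome.

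Third, the outcome is exploratory and no power is claimed for it. That limits the consequence but does not make the definition usable.

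Fourth, a reader might infer that leaving prior utilization out is an error, or that it biases the arm comparison. The documents do not support either. Utilization is a forward-looking outcome in a randomized trial, chance imbalance is already allowed for in the type I error rate, and the plan adjusts for four covariates including chronic illnesses. Nor do the documents state that prior-year data are available: Section 4.1 asks only for registration and an appointment that day, and Section 3(a) is silent on earlier periods.

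**Conclusion.** The point holds for the proxy and living-will part of advance care planning. As worded it is a status with no requirement of newness, no window and no baseline check, unlike primary components 1 and 3. Taken literally it multiplies the arm difference by (1 − b). Under the stated assumptions this leaves power of 40/22/13%, where a restricted definition would give 75/62/46%. It is dilution, not bias. The direction is certain for any b above zero if the wording is followed literally; the size depends on assumed rates that the protocol does not supply.

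Adjusting for prior-year utilization is a worthwhile precision improvement, probably small to modest, and not the correction of a fault. Neither matter touches the primary outcome or the sample size.

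**What to change.** In Section 3(c), count a proxy or living will only if it is first recorded after the randomization visit and within a stated window (for example the 90 days used in Section 9.4.1), among patients with none on file at randomization. Apply the same window to social-work and Alzheimer's Association referrals. Status at randomization is fixed before allocation, so the restricted comparison is still a randomized one.

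As a separate, optional step, extract utilization for the 12 months before randomization from the same EMR and claims sources where available, and pre-specify it as an added covariate in the Section 9.5 adjusted utilization models.

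The cost is a few sentences of text and an earlier date range on an extraction that is already planned. The downsides are a smaller denominator for proxies and living wills (432, 324 or 216 per arm in the table above) and possibly incomplete prior-year data for recently registered patients, for which the plan should state a handling rule.
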